## **V. Study Procedures**

### **Design Overview**

The proposed study is a randomized design in which Tribal College smokers will receive one of two internet-based interventions: 1) a culturally and individually tailored, interactive smoking cessation intervention (**I-ANBL**); or 2) internet-based healthy diet -fruit and vegetable consumption intervention (**I-FV**). Participants in both groups (I-ANBL and I-FV) will be offered pharmacotherapy (e.g. varenicline or bupropion or NRT). The primary outcome of interest will be biochemically verified continuous abstinence at 6 months. Secondary endpoints include number of quit attempts and number of cigarettes smoked (among continuing smokers), pharmacotherapy utilization, and the number of completed web-sessions. We will also examine the marginal cost-effectiveness of the intervention.

We propose the adaptation and testing of a culturally tailored smoking cessation program for tribal college students. We will finish developing the program using an iterative, CBPR process that we have used in the past to develop a successful smoking cessation program for AI.

The study will be done in three phases over a five-year period. Phase 1 will include adaptation of the program and tailored materials, including assessments of the website for scientific

accuracy, readability, cultural appropriateness, and navigability; Phase 2 will be to conduct the randomized trial and Phase 3 will consist of data analysis and dissemination.

Participants will be recruited from a Tribal college.

**Pharmacotherapy:** The PI of this study along with our AI community members agreed that all participants (I-ANBL and I-FV arms) had to be offered pharmacotherapy (varenicline or bupropion or NRT) as a component of the study design. This decision was a collaborative one between the AI tribes and the investigators who have worked with this population. The AI community will not accept placebo treatment, therefore, the interventions would not be acceptable or feasible to potential participants if a placebo was part of the study design.

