How the student compares to individuals who are abstinent (normative feedback); 6) maintenance of smoking abstinence. The computer expert system will draw from a bank of several hundred messages addressing different levels of cultural, psychosocial, and environmental factors affecting smoking cessation. Intervention participants will also receive tip sheets addressing barriers specific to American Indian smokers and quitting (as identified during our formative research and Phase 1 of the study).

**Educational Curriculum:** We will adapt the ANBL materials for the tribal college population through the planned focus groups in Phase I of this study. Previous participants in formative research have stressed that cultural issues must be ingrained within the program and its accompanying education materials, not given "lip service" by putting pictures of AI people on otherwise "white" materials. We will continue to follow this guideline as we modify the materials. We will begin our educational materials modification with our current educational materials for ANBL (*see appendix*). Topics will be modified based on student input.

**Pharmacotherapy:** Pharmacotherapy is recommended for smokers trying to quit. We plan to give participants in our cessation program a choice of varenicline, bupropion, nicotine replacement therapy or no pharmacotherapy. We choose to give our participants a choice because our experience shows that we would be unlikely to recruit AI participants into a trial that requires pharmacotherapy use. Many AI are unwilling to use Western pharmacotherapy at all and others are unwilling to participate in a "drug trial", particularly if randomization is involved. All participants requesting pharmacotherapy must be medically cleared prior to receiving it.

The prescription medications (Chantix and Bupropion) and over-the-counter NRT (patch, gum, and lozenge) will be stored at KUMC in locked cabinets. KUMC will be responsible for mailing requested medications to the Polson Tribal Clinic in Polson, MT. After getting medical clearance from on-the-ground physician, participants will pick up a one month supply of study medication at the clinic. All the participants will be monitored weekly via web based system for any potential adverse events.

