**Participant Incentives:** Incentives will be identified by focus group participants, CAB members, and Native research team members. For ANBL, we have used things like quit kits (hard candy, toothpicks, etc.), stress balls, flute music CD’s for relaxation, and Rez-robics® (aerobic dance videos that include pow wow and traditional dance), among other things. We will provide participants with gift cards for participating in the research. At baseline, we will give participants \$20 gift cards for survey participation. At 12-weeks and 6-months, we will give participants \$40 gift cards for survey participation. We will also give participants a \$10 gift card for providing saliva for cotinine analysis at the time points above. In addition to the above incentives, participants will also receive a \$10 gift card if they complete at least 5 of the weekly web sessions. If the participants complete all 8 weekly web sessions they will receive a \$20 gift certificate. All participants will be asked to provide saliva at baseline, 12-weeks, and 6-months. We ask for repeat samples from all participants for two reasons: (1) nicotine metabolism of smoking has not been previously examined and we plan to look at decreases in use, as well as quitting; and (2) we do not want some participants to be able to obtain additional incentives because we do not want to bias our results. We do not anticipate a problem with participants’ willingness to provide saliva; our ANBL programs have a 100% participation rate in this, even though it is voluntary for participants to provide saliva.

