- Internet Session 1:** Participants will be asked to log into the website prior to the first session to allow for any problems with the site to be fixed prior to sessions starting. Participants who decide to take any study medication will need to visit the Polson Tribal Clinic in Polson, MT to pick up a one month supply of study medication. Any unused NRT or medication will be dropped off at the clinic and then mailed back to the research assistants by the clinic staff. The study physician will be available to answer additional

questions. Beginning with this session and continuing through all sessions. Topics we anticipate covering include, but are not limited to: preparing to quit, dealing with cravings, support systems, traditional tobacco, stress reduction, weight management, and staying quit, along with other topics determined during program development. For each session, the tribal college student will begin the session by answering a series of questions to produce an individually-tailored report that will be provided on the screen at the end of each week's session so that the smoker can work on strategies during the week before the next internet session. Estimated time for the web session is 30 minutes.

- **Internet Sessions 2-8:** *The second session is the quit date for all participants in the group.* Weekly procedures will follow the same format as for the first session. At the session dealing with traditional tobacco, participants will be asked to talk about their own use, though they will not be required to do so because this is not always culturally appropriate. Participants will be asked to fill out weekly brief surveys about their use of tobacco during the week; e-mail reminders will be sent. Participants will also be asked to fill out brief session evaluations on-line after each session; e-mail reminders will be sent for these as well. Session evaluations will go directly into a separate database that will be de-identified; participants will be told about this database to encourage more truthful responses.
- **Weeks 9-11:** Participants will receive one individual email per week from a research assistant.
- **Final Session- End of Treatment (Week 12):** Session content procedures will follow the same format as for other sessions. All participants, regardless of smoking status will receive a certificate of achievement for completing the program and will be asked to submit a saliva sample.

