## Measures

**Schedule of Assessments:** The table below represents our preliminary listing of outcome assessments, based on measures used for ANBL and preliminary discussions with community members. During year one of the project, we will work closely with our community partners to refine all measures and potentially add or subtract some of them. Our community partners will have final say on all measures to be used, including whether we use standard measures validated in other populations or modify for our community.

Measures Week	1	2	3	4	5	6	7	8	12	6 mo
Primary Outcome										
The primary endpoint for the study will be biochemically (salivary cotinine) verified point prevalence abstinence, defined as no smoking for the previous 7 days, at the 6-month follow-up. This definition is based on recent consensus statements from the Society for Research on Nicotine and Tobacco Subcommittee on Abstinence Measures.	X								X	X
Biochemical Validation	X								X	X
Pharmacotherapy Use		X	X	X	X	X	X	X	X	
Demographics Tribal affiliation, age, gender, marital status, income, year in school	X									
Smoking behavior										
Traditional use of tobacco	X	X	X	X	X	X	X	X	X	X
Smoking history (age of initiation)	X									
Quitting history (length of most recent quit attempt, number of quit attempts in the past year)	X									
Self-reported Smoking status (number of cigarettes/day)	X	X	X	X	X	X	X	X	X	X
Nicotine Dependence - The Fagerstrom Test of Nicotine Dependence will be used to measure nicotine dependence. 	X								X	X
Self-efficacy	X			X				X	X	X
Motivation	X			X				X	X	X
Environmental factors										
Household structure	X								X	X
Social support	X								X	X

Exposure to others who use tobacco in any form	X			X		X			X	X
Exposure to tobacco marketing	X			X		X			X	X
Psychosocial factors										
Depression using the CES-D, 10-item. 	X		X		X		X		X	X
Negative Affect from the Positive and Negative Affect Scale (PANAS) , 	X		X		X		X		X	X
Nicotine Withdrawal using the Minnesota Withdrawal Scale (MNWS) 	X		X		X		X		X	X
Craving using the Brief Questionnaire of Smoking Urges (QSU-Brief) , 	X		X		X		X			
Treatment Factors										
Satisfaction with interactive website					X				X	X
Satisfaction with session topics		X	X	X	X	X	X	X	X	
Satisfaction with session educational materials	X	X	X	X	X	X	X	X	X	

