### **Primary Aim/Hypotheses:**

1. To test the effectiveness of the **I-ANBL** compared to the **I-FV** on smoking cessation among tribal college smokers.

Hypothesis 1: At 6 months, participants in the **I-ANBL** group will show higher 7-day point prevalence abstinence rates than those in the **I-FV** group.

We will compare the salivary cotinine verified prevalence abstinence rates at 6 months between the two groups using logistic regression. For our primary comparison, we will conduct per-protocol analyses on (a) only the participants who complete the study, as well as intent-to-treat analyses on (b) all subjects by imputing the dropouts as smokers and (c) all subjects by using the Markov Chain Monte Carlo (MCMC) imputation technique. In (c), the missing data related to attrition can be reasonably assumed to be missing due to known characteristics of our database (i.e., missing at random). We will create a large number of (e.g., 200) complete datasets via expectation-maximization algorithm as prior estimates for the MCMC procedure; and then combine the analysis outcomes from each complete dataset to make valid statistical inferences. To evaluate secondary endpoint, we will compare the salivary cotinine verified prevalence abstinence rates between the groups at Week 12 (end of pharmacotherapy). Finally, as we have no preliminary estimates of relapse based upon timeline follow-back, we will conduct explanatory, failure analyses to compare the time to relapse between the groups. We will calculate failure function (cumulative probability of smoking cessation as a function of time) and fit Cox regression models to the 6-month self-report data on smoking status.

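### The Week 12 abstinence comparison is verified by cotinine alone at the end of treatment, so participants still using trial-supplied nicotine replacement cannot be verified if the definition is read literally

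*Protocol*

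**What the plan says.** All references are to Section V of the protocol.

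- **Endpoint.** Primary Aim/Hypotheses adds a secondary comparison: "we will compare the salivary cotinine verified prevalence abstinence rates between the groups at Week 12 (end of pharmacotherapy".
- **Marker.** The schedule under Measures reads: "The primary endpoint for the study will be biochemically (salivary cotinine) verified point prevalence abstinence, defined as no smoking for the previous 7 days". Biochemical validation is marked at Weeks 1 and 12 and at Month 6. No other marker is named for this trial.
- **Medication.** Design Overview: "Participants in both groups (I-ANBL and I-FV) will be offered pharmacotherapy (e.g. varenicline or bupropion or NRT". The Pharmacotherapy paragraph under I-ANBL Interactive Individual Sessions offers "a choice of varenicline, bupropion, nicotine replacement therapy or no pharmacotherapy" and lists patch, gum and lozenge as the NRT forms.
- **Sampling.** Participant Incentives: "All participants will be asked to provide saliva at baseline, 12-weeks, and 6-months". At the Week 12 session in Anticipated Flow of Participants, which the flow table marks as the close of pharmacotherapy, participants "will receive a certificate of achievement for completing the program and will be asked to submit a saliva sample". The In-Person Visit paragraph says the Week 12 and Month 6 samples are collected with mailed kits. No nicotine-free interval is set.
- **Medication record.** The schedule marks pharmacotherapy use at Weeks 2 to 8 and at Week 12, but does not link it to the abstinence definition.
- **Second use of the samples.** One stated reason for repeat saliva is that "nicotine metabolism of smoking has not been previously examined and we plan to look at decreases in use, as well as quitting".

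**The concern.** Cotinine is the metabolite of nicotine from any source. A marker of nicotine exposure is being read at a time when the trial may itself be supplying nicotine to some participants. Among people who have all stopped smoking, those still on NRT would not be verified, while those on varenicline, bupropion or nothing could be, provided they have no other nicotine source. The endpoint would then partly reflect which medication was chosen and how long it was used.

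Medication is chosen by the participant after the arm is known: the arm is disclosed at the in-person visit, and the choice is due before the second web session. Only the I-ANBL arm has sessions on coping with withdrawal and on staying quit. NRT uptake and persistence could therefore differ by arm. Equal use lowers both observed rates and costs power; unequal use biases the comparison.

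**Working it through.** **Step 1. The plan's own figure.** Sample Size and Power gives 30% v 15% at Month 6, 80% power, 5% type I error and 121 per arm. With the pooled-variance formula, two-sided, no continuity correction, and p̄ = 0.225:

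n = [1.960 × √(2 × 0.225 × 0.775) + 0.842 × √(0.30 × 0.70 + 0.15 × 0.85)]² / 0.15² = (1.157 + 0.489)² / 0.0225 ≈ 120.5, so 121 per arm.

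Power at 121 per arm is 80.2%. The figure reproduces. It belongs to Month 6; no figure is stated for Week 12.

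**Step 2. Misclassification.** Let f be the share of true abstainers whose cotinine is raised by NRT when the sample is taken. Then:

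observed rate = true rate × (1 − f)

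Assumptions:
- The Month 6 planning rates stand in for the true Week 12 rates.
- f is not in the protocol. It is varied from 10% to 50% when equal in both arms, and set at 40% v 20% and the reverse when unequal.
- Every abstainer counted in f exceeds the cut-off, which the protocol does not give.
- There are 121 per arm, and power is computed as in step 1.

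| True rates (I-ANBL v I-FV) | f (I-ANBL v I-FV) | Observed rates | Difference (points) | Risk ratio | Power |
|---|---|---|---|---|---|
| 30% v 15% | 0 v 0 | 30% v 15% | 15 | 2.0 | 80% |
| 30% v 15% | 10% v 10% | 27% v 13.5% | 13.5 | 2.0 | 75% |
| 30% v 15% | 20% v 20% | 24% v 12% | 12 | 2.0 | 68% |
| 30% v 15% | 30% v 30% | 21% v 10.5% | 10.5 | 2.0 | 61% |
| 30% v 15% | 50% v 50% | 15% v 7.5% | 7.5 | 2.0 | 45% |
| 30% v 15% | 40% v 20% | 18% v 12% | 6 | 1.5 | 26% |
| 30% v 15% | 20% v 40% | 24% v 9% | 15 | 2.67 | 89% |
| 30% v 30% | 40% v 20% | 18% v 24% | −6 | 0.75 | not applicable |

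Example: 0.30 × (1 − 0.40) = 0.18 and 0.15 × (1 − 0.20) = 0.12.

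On the odds-ratio scale of a logistic model, equal f does less harm. The true odds ratio is (0.30/0.70)/(0.15/0.85) = 2.43. At f = 30% it is (0.21/0.79)/(0.105/0.895) = 2.27.

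**Step 3. Dependence on time since last NRT.** Residual share = 0.5^(hours / half-life). With an assumed cotinine half-life of 12 to 24 hours, 1.6% to 12.5% of the on-NRT level remains after 72 hours, and under 1% after 168 hours. A participant who stopped several days before sampling is largely unaffected; one who used NRT that day or the day before is not.

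**The case against.** A reader might infer that abstinent NRT users are coded as smokers by design. The protocol does not say that. It gives no cut-off and no rule for a raised cotinine with reported NRT use; the only people it expressly imputes as smokers are dropouts. A statistical analysis plan that is not shown could contain an exception.

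Nor does the protocol establish that many participants are on NRT when they give saliva. Week 12 is labelled the end of pharmacotherapy, the kits are mailed so the collection day is not fixed, and the medication paragraphs describe pick-up of one month's supply without mentioning refills. Against this, pharmacotherapy use is scheduled for recording through Week 12, and nothing requires an interval after the last NRT.

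The rates in the table are Month 6 planning figures. The only 12-week rate in the protocol is the first pilot's 80% smoke free, against about 25% at 6 months. With equal NRT use the risk ratio does not move and the odds ratio moves little. A reader might also infer that the endpoint works against I-ANBL; the reversed scenario shows that it could equally favour it.

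The outcome is minor in the plan: it is not in the Secondary Aims or in the Design Overview list of secondary endpoints. The reduction in smoking under Hypothesis 1A is measured by cigarette counts, so the remark about decreases in use has no planned cotinine analysis behind it.

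These points limit the size of the problem and the certainty about it. They do not remove the conflict between marker, sampling time and supplied medication, all of which the protocol fixes. A cut-off alone cannot separate the two sources of nicotine.

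**Conclusion.** The concern holds in limited form. If the Week 12 definition is applied as written, an abstinent participant still using NRT at sampling cannot be verified, and an equally abstinent varenicline or bupropion user can. The number affected is unknown. Under the stated assumptions, power falls from 80% to between 75% and 45% when 10% to 50% of quitters are on NRT equally in both arms. When use differs by arm, the observed difference can shrink to 6 points, the risk ratio can rise to 2.67, or a false 6-point deficit can appear with no true effect. These figures illustrate the mechanism; they do not forecast what this trial will see.

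The conclusion concerns the Week 12 comparison only. A reader might extend it to the Month 6 primary endpoint, but the protocol ends supplied medication at Week 12, about three months earlier, so this argument does not reach it. The point should be corrected before analysis; it does not threaten the trial's main conclusion.

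**What to change.** In Primary Aim/Hypotheses, state for Week 12 that:

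1. in a participant whose Week 12 pharmacotherapy record shows NRT in the past 7 days, a positive cotinine alone does not overrule self-reported 7-day abstinence;
2. everyone else is verified by cotinine;
3. the strict cotinine-verified rate is reported alongside as a sensitivity analysis, with NRT use at Week 12 by arm;
4. Week 12 cotinine is not read as a measure of reduced smoking in NRT users.

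The cost is protocol and analysis wording, with no new sample or visit. The schedule already includes a Week 12 pharmacotherapy item but does not show its content, so it should be checked that the item identifies NRT and the past 7 days.

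The drawback is real. Status in current NRT users would rest on self-report, so the strength of verification would still depend on the medication chosen. An NRT user who also smokes and misreports would pass, and if NRT use differs by arm this could bias the comparison the other way. Both rates must therefore be shown: agreement between them would be reassuring, and disagreement would show how far the result depends on the rule.

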### **Formative Research for this Proposed Study**

Our American Lung Association (ALA) funded (SB-11343-N, PI: [name]) formative research addressed the important and neglected public health problem of smoking among AI/ANs. The goal of this project was to identify culturally acceptable and potentially effective methods for smoking cessation in this underserved and high risk population.

**Focus Groups:** We conducted six focus groups with AI/AN smokers (N=41) at HHC to determine facilitators and barriers to smoking cessation, and the feasibility of developing a smoking cessation program for a heterogeneous AI/AN population. These participants represented 23 different nations.

Participants discussed three major themes: traditional use of tobacco, quitting and quit attempts, and smoking cessation program. We currently have two published manuscripts (see appendix) and two national presentations based on these data. Based on results of these focus groups and meetings with AI/AN community members, we began creation of a culturally-tailored smoking cessation program.

**Feasibility/Compliance Pilot:** Based on the findings from our focus groups, previous smoking cessation programs developed by members of our team, and the Second Wind program, we began creation of the ANBL program. The pilot version was developed with direct community involvement in an iterative process that included weekly meetings with AI/AN colleagues and community members. It included group sessions and individual phone calls, but used different timing and frequency, as well as a draft curriculum. The name, “All Nations Breath of Life” and slogan, “Light Up a New Way,” were selected from community members’ submissions to a contest. We completed a pilot project to test the implementation feasibility and participant compliance of ANBL at HHC with 30 AI/AN smokers. All participants were offered either nicotine patch or bupropion for free. At the end of the 12 week program, 80% of our participants were smoke free. At 6 months, approximately 25% of the participants remained abstinent (verified through carbon monoxide test). At 6 months, our retention rate was approximately 80% for this pilot. During our pilot studies, we collected data on the characteristics of smokers at HHC.

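### The exploratory time-to-relapse analysis has no relapse dates after week 12: the schedule lists neither a timeline follow-back nor any smoking-status assessment between week 12 and month 6

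*Protocol*

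**What the plan says.** **Analysis.** Under Primary Aim/Hypotheses the protocol says "we will conduct explanatory, failure analyses to compare the time to relapse between the groups". It will compute a failure function and "fit Cox regression models to the 6-month self-report data on smoking status". The reason given for treating this as exploratory is that "we have no preliminary estimates of relapse based upon timeline follow-back".

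**Data.** In the Measures table, the row beginning "Self-reported Smoking status (number of cigarettes/day" is marked at weeks 1 to 8, week 12 and 6 months. No row names timeline follow-back or a relapse date. The quitting-history row, which includes the length of the latest quit attempt, is marked at week 1 only. The text above the table calls the list preliminary and allows measures to be added or removed during year one.

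**Contacts.** Under Anticipated Flow of Participants, session 2 is the quit date. For sessions 2 to 8, "Participants will be asked to fill out weekly brief surveys about their use of tobacco during the week". For weeks 9 to 11, "Participants will receive one individual email per week from a research assistant", with no survey described. No contact is described from week 12 to month 6, and at month 6 the participant is asked about current smoking status.

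**Pilot.** Under Formative Research for this Proposed Study, "At the end of the 12 week program, 80% of our participants were smoke free". About 25% were abstinent at 6 months by carbon monoxide test, with about 80% retention, among 30 smokers.

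**The concern.** A Cox model for time to relapse needs an event time. As scheduled, that time can only be the first assessment at which the participant reports smoking. The assessments are a week apart up to week 8 and four weeks apart to week 12. Nothing follows until month 6. The last interval is longer than all the earlier post-quit follow-up together.

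What a time-to-relapse analysis adds to the month-6 abstinence comparison is information on when people return to smoking. The months after pharmacotherapy ends at week 12 are an obvious period to ask about. If every relapse in that period is recorded at month 6, the analysis cannot distinguish early from late relapse within it. The resulting block of tied event times can also distort the hazard ratio.

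**Working it through.** **1. The plan's own figure.** No figure is given for the relapse analysis. The only power figure is 121 per arm for 30% against 15% abstinence at month 6. With mean rate 0.225 and a two-sided 5% level (sidedness is not stated):

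n = [1.960 × √(2 × 0.225 × 0.775) + 0.842 × √(0.30 × 0.70 + 0.15 × 0.85)]² / 0.15² ≈ 120.5, so 121.

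This reproduces and is not touched by the present point.

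**2. Length of the unobserved window.** Take month 6 as week 26 and the quit date as week 2. The window is 26 − 12 = 14 weeks, out of 26 − 2 = 24 weeks.

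**3. What the pilot suggests.** Per 100 participants, counting everyone as having quit at the start:

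- Not smoke-free at week 12: 20. Further net loss by month 6: 80 − 25 = 55.
- Share of failures in the window: 55 / (55 + 20) = 73%.
- If all 20 not retained were week-12 quitters and are not counted as relapses: 35 / (35 + 20) = 64%.
- As a fraction of week-12 quitters, net loss is 55/80 = 69%. Without those 20 it is 35/80 = 44%, or 35/60 = 58% of those still followed.

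**4. What it would be in this trial.** With month-6 abstinence p6 at the design rates and week-12 abstinence w12 assumed, the share of relapses recorded at month 6 is (w12 − p6) / (1 − p6):

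| Assumed w12 | I-ANBL (p6 = 30%) | I-FV (p6 = 15%) |
|---|---|---|
| 40% | 14% | 29% |
| 50% | 29% | 41% |
| 60% | 43% | 53% |
| 70% | 57% | 65% |
| 80% | 71% | 76% |

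The share passes one half when w12 exceeds (1 + p6)/2, that is 65% for I-ANBL and 57.5% for I-FV. The protocol states no expected week-12 rate.

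**5. Effect on the hazard ratio.** The simulation used 400 trials of 150 per arm with no dropout and everyone quitting at week 2. Hazards were proportional, with true ratio ln 0.30 / ln 0.15 = 0.635. Relapse times were either exact or recorded at weeks 3 to 8, 12 and 26. Entries are estimated hazard ratio and power at two-sided 5%:

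| Control w12 | Relapses at month 6 | Exact dates | Grid, Breslow | Grid, Efron |
|---|---|---|---|---|
| 30% | 21% | 0.639, 92% | 0.676, 86% | 0.643, 92% |
| 50% | 45% | 0.639, 94% | 0.701, 82% | 0.648, 90% |
| 70% | 68% | 0.633, 94% | 0.742, 68% | 0.658, 90% |
| 80% | 78% | 0.634, 94% | 0.765, 54% | 0.666, 89% |

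**6. What no tie method restores.** Suppose a control participant relapses in week 13 and an I-ANBL participant in week 25. Both are abstinent at week 12 and smoking at month 6, so both enter the model with the same event time. The 12-week difference is not in the data.

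**The case against.** The protocol names timeline follow-back in the sentence that introduces this analysis. The 6-month self-report could therefore mean dates recalled over six months, and relapses would then not be tied. The schedule is openly provisional and its rows are broad headings, so a missing item is weak evidence that none will be asked. Tie handling and the exact survival model may be settled in a statistical analysis plan that is not shown. The analysis is exploratory, with no hypothesis or power claim.

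Much of this stands. It means the protocol leaves the source of event times open, not that it excludes dated recall. It does not remove the mismatch: one section refers to a method that the schedule does not collect. An analysis plan can choose a model but cannot supply dates that were never asked for.

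A reader might go further and infer that most relapses in this trial will share one time because the pilot lost 69% of its quitters in the window. The documents do not support that. The 69% is net loss of abstinence in 30 people in an in-person programme. It may include dropout, and no biochemical check is stated for week 12. Whether most relapses fall in the window here depends on an unstated week-12 rate. A reader might also infer that the analysis collapses to the month-6 yes/no comparison or must lose much power. With Efron ties and proportional hazards the loss is small, so that does not hold in general either.

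**Conclusion.** The point holds in limited form. As scheduled, relapses after week 12 are dated only to a window of about 14 weeks and share one recorded time, and the timeline follow-back mentioned in the analysis section is not in the schedule. On the pilot's pattern 64% to 73% of failures would be affected. At the design rates the share ranges from 14% to 76% across arms for week-12 abstinence between 40% and 80%.

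A difference in relapse timing confined to the window cannot be detected. Under proportional hazards, in the settings simulated, a true ratio of 0.635 is estimated at 0.68 to 0.77 with Breslow ties and 0.64 to 0.67 with Efron.

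These figures assume that month 6 is week 26, that everyone quits at week 2, that later non-abstinence counts as relapse, and that no relapse dates are collected. Severity is low: the primary endpoint, the week-12 comparison and the sample size are unaffected.

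**What to change.** Add the timeline follow-back to the week-12 and month-6 web surveys and list it in the Measures table. Two items suffice: the date of first smoking after the quit date, and the date regular smoking resumed. State under Primary Aim/Hypotheses which of the two dates is the event time.

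If the items are not added, replace the Cox model there with a discrete-time or interval-censored model on the scheduled assessments. This treats the grid honestly and removes the dependence on tie handling, but it does not recover timing within the window.

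The cost is one or two questions in two existing surveys, which fits the year-one refinement of measures the protocol already plans, plus a sentence in the analysis section. The downside is recall error in the dates, over at most about 14 weeks for the month-6 survey.
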